5.2 Exclusion Criteria

1. Receiving $>$ 1 anti-epileptic drug for seizures
2. Sustained (>4 hours) heart rate $>$ 180 beats per minute
3. Known major congenital anomaly
4. Any condition which would make the participant, in the opinion of the investigator, unsuitable for the study

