7.2 Participant Discontinuation/Withdrawal from the Study

The participant's parent or guardian may withdraw voluntarily from participation in the study at any time. The participant's parent or guardian is not obligated to state the reason for withdrawal. The reasons for withdrawal, or failure to provide a reason, must be documented by the investigator on the completion/ withdrawal section of the electronic case report form (CRF). We will also document missing values in the database for subjects who withdraw from the study.

An investigator may discontinue or withdraw a participant from the study for the following reasons:

- If any clinical AE, laboratory abnormality, or other medical condition or situation occurs such that continued participation in the study would not be in the best interest of the participant
- Disease progression which requires discontinuation of the study intervention
- If the participant meets an exclusion criterion (either newly developed or not previously recognized) that precludes further study participation (e.g., prescribed a second anti-epileptic drug for seizures)

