8.3.8 Events of Special Interest

1. Seizures will be defined by the receipt of > 1 AED, as we are interested in identifying seizures which are difficult to control.
2. Necrotizing Enterocolitis - Bell Stage II or III⁵⁷

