9 STATISTICAL CONSIDERATIONS

9.1 Statistical Hypotheses

- **Pharmacokinetics**

We hypothesize that drug clearance will be $\geq 20\%$ lower than expected for gestational age and birth weight as a result of HIE and therapeutic hypothermia.

- **Safety**

We hypothesize that frequency of seizures in both treatment cohorts will be within 20% of published results of neonates treated with therapeutic hypothermia in the NICHD Total Body Hypothermia for Neonatal Encephalopathy trial.⁵

- **Preliminary effectiveness**

We hypothesize that the risk ratio for an abnormal MRI prior to discharge will be favorable, i.e., between 0.7 and 1.1 in treated neonates compared to published results of neonates treated with therapeutic hypothermia in the NICHD Total Body Hypothermia for Neonatal Encephalopathy trial.⁵

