9.2 Sample Size Determination

- **Pharmacokinetics**

A sample size of 9 neonates in each dosing cohort will be powered ($\geq 80\%$) to target a 95% confidence interval within 60% and 140% of the geometric mean estimate of clearance (assuming 36% between subject variability in clearance, which is based on existing literature of caffeine PK in neonates).⁵⁸⁻⁶⁰

- **Safety**

The frequency of seizures in the treated group of the NICHD trial was $\sim 40\%$.⁵ Estimation of the probability of seizures in our study will be based on the combined sample of 18 patients. For comparison with historical data, the null hypothesis that the frequency of seizures is 40% will be rejected if 11 or more adverse events (in 18 patients) are observed. The event probability will be no wider than 21% on each side of the point estimate and this will provide a power of 86%. The alternative hypothesis is that the frequency of seizures is $> 61\%$ or $< 19\%$ in our study (i.e., $> 21\%$ on either side of the point estimate of 40%).

- **Preliminary effectiveness**

This is an exploratory aim and will not be sufficiently powered to detect a significant reduction in brain injury on MRI. However, we estimate that there will be a trend toward risk reduction of brain injury in enrolled neonates compared to treated neonates in the NICHD trial.

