9.4.3 Analysis of the Secondary Endpoint(s)

- **Preliminary Effectiveness**

We will use MRI brain images from enrolled neonates to assess the severity of brain injury according to the scoring strategy used in the NICHD trial: 0 (normal MRI), 1A (minimal cerebral lesions), 1B (extensive cerebral lesions), 2A (basal ganglia thalamic injury), 2B (2A with cerebral lesions), and 3 (hemispheric devastation). We will dichotomize these results into normal and abnormal and use logistic regression to compare neonates in cohorts 1 and 2 to treated neonates in the NICHD trial to calculate a risk ratio for abnormal MRI with 95% confidence

intervals, adjusting for potential confounders such as severity of encephalopathy and presence of seizures.

We will use the composite cognitive, language, and motor scores on the Bayley-III at the 18-24 month follow-up visit to assess NDI. We will define NDI as any of the following: composite cognitive, language, or motor score < 85, hearing impairment requiring hearing aids, a diagnosis of blindness, or GMFCS level ≥ 3 . We will use logistic regression to compare neonates in cohorts 1 and 2 to treated neonates in the NICHD trial to calculate a risk ratio for NDI with 95% confidence intervals.

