9.4.4 Safety Analyses

We will collect information on adverse events (AEs) during and after study drug administration. Seizures will be AE of special interest and defined by the receipt of > 1 AED. We will summarize AEs by organ system and report descriptive statistics of laboratory values. We will correlate caffeine exposure with seizure activity and NEC following the first dose of caffeine.

Following the follow-up period in the final cohort 1 participant, there will be an interim safety analysis performed by an independent safety monitor (ISM) with training in neonatology and experience in conducting clinical trials who is not otherwise associated with the study. We will halt enrollment during this analysis. If there is > 1 serious adverse events (SAEs) related to the drug in any cohort, the study will be temporarily halted for an *ad hoc* safety review.

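### Section 9.1 defines a favorable MRI risk ratio as 0.7 to 1.1, so no effect or slightly more injury meets the hypothesis and a large reduction does not

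*Combined protocol and SAP*

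**What the plan says.** Section 9.1 (preliminary effectiveness) predicts that "the risk ratio for an abnormal MRI prior to discharge will be favorable, i.e., between 0.7 and 1.1", with the cooled arm of the NICHD trial as comparator. Section 8.1.6 codes a normal MRI as 0 and an abnormal one as 1, so a ratio above 1 means more injury than cooling alone. Section 2.2 gives the comparator's abnormal rate as 48%, against 65% without cooling. The synopsis (1.1) states the aim as reducing brain injury. Section 9.2 calls the aim exploratory and not sufficiently powered, then adds that "we estimate that there will be a trend toward risk reduction of brain injury in enrolled neonates".

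Section 9.4.3 uses logistic regression "to calculate a risk ratio for abnormal MRI with 95% confidence" limits, "adjusting for potential confounders such as severity of encephalopathy and presence of seizures". On seizures, 9.4.4 states: "Seizures will be AE of special interest and defined by the receipt of > 1 AED". Sections 8.3.8 and 9.4.4.1 define them the same way. Receipt of more than one anti-epileptic drug for seizures is an exclusion criterion in 5.2. Section 7.2 illustrates meeting an exclusion criterion during the study with "e.g., prescribed a second anti-epileptic drug for seizures".

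**The concern.** The sentence in 9.1 does not merely offer a range; it says what favorable means. Both ends of that range are then a problem. The upper limit admits estimates at or above 1, which 9.2 would not call a risk reduction. The lower limit leaves out the results that the aim most hopes for. No section gives a non-inferiority argument for 1.1, a reason for stopping at 0.7, or a statement that ratios under 0.7 also qualify.

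At stake is the wording of the MRI result. A report that follows 9.1 literally would describe 9 abnormal scans of 18 (50%, above the 48% comparator) as favorable and 5 of 18 (28%) as not meeting the hypothesis. Sections 2.2 and 4.2 present this study as the first step towards a larger trial, so that description may be carried forward.

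The secondary concern is the seizure covariate in 9.4.3. Under the protocol's only definition, it is an event that entry criteria exclude at baseline and that is also a safety outcome of special interest. Adjusting for an event that follows dosing can remove part of a treatment effect on MRI, in either direction.

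**Working it through.** **Origin of the band.** The plan gives no derivation, so there is no figure to reproduce. Two candidates do not explain it:
- Cooling versus control is 0.48/0.65 = 0.74, which is a different comparison.
- At 8 of 18 abnormal, the exact 95% limits for the proportion are 0.215 and 0.692. Divided by 0.48, these give risk ratios of 0.45 and 1.44, so the band is not a confidence interval at this sample size.

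**Inputs.** n = 18 (two cohorts of 9; 4.1, 6.1.2); one MRI per infant (section 3 says every cooled neonate has one before discharge); comparator p0 = 0.48 (2.2), held fixed because the documents give no denominator; band 0.7 to 1.1 (9.1). The ratio is crude, not the adjusted one of 9.4.3.

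**Which counts qualify.** Estimated RR = (k/18)/0.48:
- k = 5: 0.579
- k = 6: 0.694
- k = 7: 0.810
- k = 8: 0.926
- k = 9: 1.042
- k = 10: 1.157

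Only k = 7, 8 and 9 lie in the band. The count k = 6 is borderline: it enters if ratios are rounded to one decimal, or if the unrounded comparator rate is about 47.6% or lower.

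**Chance of meeting each criterion.** k ~ Binomial(18, 0.48 × true RR). The band requires k = 7 to 9; RR < 1 requires k ≤ 8. At true RR 1.0, for example, 0.1404 + 0.1782 + 0.1828 = 0.501.

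| True RR | In band (k = 7–9) | In band with k = 6 rounded in | Estimate below 1 (k ≤ 8) |
|---|---|---|---|
| 1.1 | 42.0% | 46.9% | 31.7% |
| 1.0 | 50.1% | 59.0% | 47.5% |
| 0.9 | 52.0% | 65.6% | 63.8% |
| 0.8 | 46.5% | 64.3% | 78.1% |
| 0.7 | 35.5% | 55.1% | 88.8% |
| 0.6 | 22.5% | 40.5% | 95.3% |
| 0.5 | 11.3% | 24.5% | 98.5% |

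The band column is nearly flat from 1.0 to 0.8 and then falls as benefit grows. The last column rises steadily with benefit.

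**Sensitivity (assumed ranges).**
- With 16 to 18 MRIs, the in-band chance is 47–52% at RR 1.0, 36–44% at 1.1 and 11–20% at 0.5.
- With a comparator of 50 to 100 sampled infants and n = 18, it is 49–52%, 43–44% and 17%.
- The chance that the estimate is below 1 when there is no effect is 46.6% for n = 16, 56.6% for n = 17 and 47.5% for n = 18.

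**Seizure covariate.** No arithmetic applies. Sections 8.3.8, 9.4.4 and 9.4.4.1 define seizures as more than one anti-epileptic drug. Section 5.2 excludes infants already in that state. An enrolled infant who has the covariate as defined has therefore normally acquired it after enrolment.

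**The case against.** The best defence is that 9.1 states a prediction, like its neighbours on clearance and seizures, and not a pass mark. Most of the band (0.7 to 1.0) agrees with 9.2. The aim is exploratory and unpowered (8.1.6, 9.2), and 9.4.3 already reports an interval. This stands as to weight. A reader might infer that the band is a success rule on which the next trial depends; no section ties any decision to it. It does not rescue the sentence, which equates favorable with the band.

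A reader might also infer that the band favors an inert drug over any effective one. The table does not support that. At true RR 0.9 the band is met slightly more often than at 1.0, and with 6 of 18 rounded in, 0.8 also exceeds 1.0. The inversion is clear only for large effects, and halving injury on top of cooling would exceed what cooling itself achieved (0.74). Also, with 18 MRIs the only attainable crude ratio in the band above 1 is 1.04.

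A criterion of RR < 1 does not protect against a null drug either: at n = 17 it is met 57% of the time under no effect, against 47% for the band. This is correct and shapes the fix.

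On seizures, the covariates in 9.4.3 are given as examples, and seizures before dosing may be meant. Concluding that adjustment will hide a caffeine effect would go beyond the text; the documents support only a request to specify.

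**Conclusion.** The wording in 9.1 is wrong as it stands. Ratios of 1.0 to 1.1 satisfy a hypothesis labelled favorable, and ratios clearly below 0.7 do not, against the aim in the synopsis and the direction expected in 9.2. Under the stated assumptions (18 MRIs, fixed 48% comparator, crude ratio), a drug that raises injury by 10% meets the hypothesis about 3.7 times as often as one that halves it (42.0/11.3). Across no effect and modest benefit (1.0 to 0.8) the band scarcely discriminates. The ordering of 1.0 and 1.1 above 0.5 holds with 16 to 18 MRIs and with a sampled comparator of 50 to 100.

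The consequence is limited to how an exploratory result is described, so this is a change to consider and not a flaw in the trial's main analyses. Confidence is high on the wording. The seizure covariate is a secondary clarification that rests partly on inference about what 9.4.3 intends.

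**What to change.** In 9.1, state a risk ratio below 1 as the hypothesised favorable direction, remove the 0.7 to 1.1 band, and say that the estimate will be interpreted only with the 95% confidence interval already planned in 9.4.3. Add that a point estimate below 1 is not evidence of benefit by itself, since it occurs about 47–57% of the time under no effect with 16 to 18 MRIs. If an expected range or a not-much-worse margin was intended, say so and justify its limits.

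In 9.4.3, limit adjustment to variables fixed before the first dose, for example Sarnat stage (recorded under 8.1.1) and anti-epileptic drug status at screening (already needed to apply 5.2). This should be conditional on the same variables being available for the comparator, which the documents do not establish.

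The cost is one sentence or two in 9.1 and one clause in 9.4.3, with no new data, visits or samples.

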9.2 Sample Size Determination

- **Pharmacokinetics**

A sample size of 9 neonates in each dosing cohort will be powered ($\geq 80\%$) to target a 95% confidence interval within 60% and 140% of the geometric mean estimate of clearance (assuming 36% between subject variability in clearance, which is based on existing literature of caffeine PK in neonates).⁵⁸⁻⁶⁰

- **Safety**

The frequency of seizures in the treated group of the NICHD trial was $\sim 40\%$.⁵ Estimation of the probability of seizures in our study will be based on the combined sample of 18 patients. For comparison with historical data, the null hypothesis that the frequency of seizures is 40% will be rejected if 11 or more adverse events (in 18 patients) are observed. The event probability will be no wider than 21% on each side of the point estimate and this will provide a power of 86%. The alternative hypothesis is that the frequency of seizures is $> 61\%$ or $< 19\%$ in our study (i.e., $> 21\%$ on either side of the point estimate of 40%).

- **Preliminary effectiveness**

This is an exploratory aim and will not be sufficiently powered to detect a significant reduction in brain injury on MRI. However, we estimate that there will be a trend toward risk reduction of brain injury in enrolled neonates compared to treated neonates in the NICHD trial.

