1 PROTOCOL SUMMARY

1.1 Synopsis

Title:	Pharmacokinetics and Safety of Caffeine in Neonates with Hypoxic-Ischemic Encephalopathy
Study Description:	This is a phase I, open-label, dose-escalating pharmacokinetics (PK) and safety study of caffeine in neonates with hypoxic-ischemic encephalopathy undergoing therapeutic hypothermia. We hypothesize that drug clearance will be $\geq 20\%$ lower than expected for gestational age and birth weight and that the incidence of adverse events will be within 20% of published results of neonates treated with therapeutic hypothermia in the NICHD Total Body Hypothermia for Neonatal Encephalopathy trial.
Objectives:	
Primary Objective: Characterize the PK of caffeine in neonates undergoing therapeutic hypothermia for hypoxic-ischemic encephalopathy (HIE).
 
Secondary Objectives: Characterize the safety of caffeine in neonates undergoing therapeutic hypothermia for HIE. Evaluate the preliminary effectiveness of caffeine in reducing brain injury in neonates with HIE.

Endpoints:	
Primary Endpoint: PK: Caffeine clearance
 
Secondary Endpoints: Safety: Adverse events Note: Seizures and necrotizing enterocolitis will be AEs of special interest Preliminary effectiveness: Death, abnormal MRI findings, neurodevelopment at 18-24 months

Study Population:	
Inclusion Criteria
 
 1. Documented informed consent from parent or guardian 2. ≥ 36 weeks gestational age at birth 3. Receiving therapeutic hypothermia for a diagnosis of HIE 4. Intravenous (IV) access 5. Postnatal age < 24 hours 
Exclusion Criteria
 
 1. Receiving > 1 anti-epileptic drug for seizures 2. Sustained (>4 hours) heart rate > 180 beats per minute 3. Known major congenital anomaly 4. Any condition which would make the participant, in the opinion of the investigator, unsuitable for the study
Phase:	1
Description of Sites/Facilities Enrolling Participants:	Up to 3 US Neonatal Intensive Care Units, including The University of North Carolina at Chapel Hill Newborn Critical Care Center

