8.3.4 Time Period and Frequency for Event Assessment and Follow-up

The occurrence of an adverse event (AE) or serious adverse event (SAE) may come to the attention of study personnel during the 7 day follow-up period.

All AEs including local and systemic reactions not meeting the criteria for SAEs will be captured on the appropriate case report form (CRF). Information to be collected includes event description, time of onset, clinician's assessment of severity, relationship to study product (assessed only by those with the training and authority to make a diagnosis), and time of resolution/stabilization of the event. All AEs occurring while on study must be documented appropriately regardless of relationship. All AEs will be followed to adequate resolution.

Any medical condition that is present at the time that the participant is screened will be considered as baseline and not reported as an AE. However, if the study participant's condition deteriorates at any time during the study, it will be recorded as an AE.

Changes in the severity of an AE will be documented to allow an assessment of the duration of the event at each level of severity to be performed. AEs characterized as intermittent require documentation of onset and duration of each episode.

The investigator will record all reportable events with start dates occurring any time after informed consent is obtained until time of discharge from the initial hospitalization.

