9.4 Statistical Analyses

9.4.1 General Approach

Analyses will be presented by treatment cohorts. There are 2 planned treatment cohorts: 1) participants receiving caffeine dosing in Cohort 1; and 2) participants receiving caffeine dosing in Cohort 2.

Descriptive statistics

Descriptive statistics such as number of observations, mean, median, standard deviation, standard error, minimum and maximum will be presented by treatment groups for continuous variables (such as age, weight, etc.). Other descriptive statistics such as counts, proportions, and/or percentages will be presented by group to summarize discrete variables (such as race, sex, etc.).

PK analysis plan

PK parameters will be estimated by population PK approach using nonlinear mixed effects modeling in NONMEM (Icon Development Solutions, [name]). The influence of covariates on PK parameters, such as gestational age, postnatal age, serum creatinine and transaminases, oliguria, and concomitant medications will be explored.

Safety

The number and percent of AEs and SAEs within each cohort will be summarized overall as well as by each Medical Dictionary for Regulatory Activities (MedDRA) system organ class and preferred term. Laboratory data will be tabulated by dose groups. Summary statistics for changes from baseline will be presented.

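### The rejection rule in Section 9.2 counts adverse events, but its null and its cut-off of 11 are for infants with seizures

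*Combined protocol and SAP*

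**What the plan says.** Section 9.2 (Safety) takes about 40% as the seizure frequency in the treated group of the NICHD trial and states that "Estimation of the probability of seizures in our study will be based on the combined sample of 18 patients". The alternative is also a seizure frequency, above 61% or below 19%. The decision rule between them is that "the null hypothesis that the frequency of seizures is 40% will be rejected if 11 or more adverse events (in 18 patients) are observed".

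The hypothesis is worded in two ways elsewhere:

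- Section 9.1: "We hypothesize that frequency of seizures in both treatment cohorts will be within 20% of published results".
- Section 1.1 (Synopsis): "the incidence of adverse events will be within 20% of published results of neonates treated with therapeutic hypothermia". Section 4.1 also speaks of adverse events, without the 20% margin.

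Section 8.3.1 defines an adverse event broadly, as any untoward occurrence whether or not it is related to the drug. Sections 8.3.8, 9.4.4 and 9.4.4.1 (item 9) define the seizure event of special interest by receipt of more than one anti-epileptic drug.

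**The concern.** The quantity tested and the quantity counted differ. The null is a proportion of infants, so its natural input is the number of infants, from 0 to 18, who had the seizure event. The rule as written takes a number of adverse events. That number is not limited to seizures, is not limited to one per infant, and can exceed 18.

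This is the plan's only numeric rule for comparing safety with historical data. If an analyst followed its words, kidney, liver or coagulation events could lead to a statement that the seizure frequency differs from 40%. The synopsis lends that reading some support. The study is open-label, so an unresolved counting unit could also be settled after the data have been seen.

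**Working it through.** **Inputs.** From Section 9.2: n = 18, null p0 = 0.40, reject at 11 or more, upper alternative 0.61, stated power 86%. The plan gives no significance level and no expected number of adverse events per infant. The adverse-event rates in steps 3 to 5 are therefore assumptions, shown as a range.

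**1. The plan's own figure.** Counting infants with seizures, power is P(X ≥ 11) for X ~ Binomial(18, p). At p = 0.61 this is 0.598, so the stated 86% is not reproduced. It matches p = 0.70, where the result is 0.859. This is a separate matter from the counting unit and is not used below.

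**2. What the cut-off is calibrated for.** For X ~ Binomial(18, 0.40):

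| Reject at | P(reject), true rate 40% |
|---|---|
| 10 or more | 0.135 |
| 11 or more | 0.058 |
| 12 or more | 0.020 |

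Eleven is the cut-off nearest a one-sided 5% test on infants with seizures.

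**3. Literal count of all adverse events.** Let m be the mean number of adverse events per infant and N ~ Poisson(18m). Then P(reject) = P(N ≥ 11).

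| m (assumed) | 18m | P(reject) |
|---|---|---|
| 0.4 | 7.2 | 0.11 |
| 0.5 | 9.0 | 0.29 |
| 0.6 | 10.8 | 0.52 |
| 0.75 | 13.5 | 0.79 |
| 1.0 | 18.0 | 0.97 |

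The 50% point is m = 0.59. If the null is true and each affected infant contributes one event, seizures alone give m = 0.4. The first row therefore leaves no room for any other adverse event.

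**4. Seizures at exactly 40% plus one other event type.** Add an independent Binomial(18, q) count to the seizure count. P(total ≥ 11) is 0.26 at q = 0.10 and 0.54 at q = 0.20.

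**5. Infants with any adverse event, each counted once.** With X ~ Binomial(18, p), P(X ≥ 11) is 0.24 at p = 0.50, 0.56 at 0.60, 0.86 at 0.70 and 0.98 at 0.80. Counting each infant once is not enough, because the event type must be fixed as well.

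**6. The shorthand reading.** If the words mean seizure events of special interest, one per infant, the count is that of step 2 and the false-rejection rate is 5.8%.

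**The case against.** The best defence is context. In Section 9.2 the historical rate, the estimand, the null and the alternative all concern seizures, and the denominator is patients. Section 9.1 names seizures, and seizures are a designated adverse event of special interest. A statistician testing a 40% seizure frequency would be unlikely to enter creatinine values. This stands, and it makes the shorthand the likelier intent. It does not change what the rule says, nor the mismatch between the synopsis and Section 9.1.

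A reader might go further and make three inferences that the documents do not support.

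- *That the rule rejects in most trials even if caffeine has no effect on seizures.* This needs both the literal reading and about 0.6 or more adverse events per infant, and the documents give no such rate. The published rates in Table 2 cannot simply be summed to supply one. Several are laboratory thresholds, and Section 8.3.1 makes a laboratory change an adverse event only if the investigator judges it clinically significant. Section 8.3.4 excludes conditions present at screening unless they worsen. Sections 1.3, 8.1.2 and 8.1.3 list kidney, liver and coagulation events separately from adverse events.
- *That repeat seizure episodes inflate the count.* Section 8.3.4 does say that "AEs characterized as intermittent require documentation of onset and duration of each episode", but that governs case-report documentation. Receipt of more than one anti-epileptic drug is in effect a yes/no status per infant.
- *That dose escalation or halting depends on this count.* Sections 9.4.4 and 10.1.6 rest those on the independent safety monitor's review and on related serious adverse events.

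The tabulation in Section 9.4.1, "The number and percent of AEs and SAEs within each cohort will be summarized overall", is descriptive and does not feed the test. It needs no change on this account.

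**Conclusion.** The concern holds as a wrong counting unit in the decision rule, together with a mismatch between the synopsis and Section 9.1. The cut-off of 11 has a known error rate, 5.8% one-sided at a true 40%, only for infants with the seizure event counted once each. On the literal reading the false-rejection rate is not determined by the plan. Under the assumed Poisson rates it is 11% at 0.4 adverse events per infant, 52% at 0.6 and 97% at 1.0. On the shorthand reading it stays near 6%.

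The literal figures rest on independent events and on assumed rates. They show how far the answer depends on the wording and do not predict this trial's result.

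Three other matters in the same section are separate and add no weight here: the 86% power that is not reproduced at 61%, the absence of a lower rejection limit to match the two-sided alternative, and whether the 40% benchmark uses the same seizure definition.

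**What to change.** In Section 9.2, restate the rejection condition as: *11 or more of the 18 infants have the protocol-defined seizure event of special interest (receipt of > 1 AED), each infant counted once*. In Section 1.1, name seizures as the outcome compared with the NICHD trial, to match Section 9.1, and use the same term in Section 4.1.

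The cost is a wording amendment, with no added infants, data or procedures. The change settles the counting unit only. The cut-off itself should be looked at again when the separate power and lower-limit questions are answered.

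### The seizure rule (reject 40% at 11 or more of 18) has 60% power at 61%, the only upper alternative named, against a stated 86%, and it cannot detect the stated alternative below 19%.

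*Combined protocol and SAP*

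**What the plan says.** Section 9.2 (Sample Size Determination, Safety) pools the two cohorts: "Estimation of the probability of seizures in our study will be based on the combined sample of 18 patients". It takes the historical rate as about 40% and gives the decision rule: "the null hypothesis that the frequency of seizures is 40% will be rejected if 11 or more adverse events (in 18 patients) are observed". It then claims precision and power together: "The event probability will be no wider than 21% on each side of the point estimate and this will provide a power of 86" per cent. The alternative follows in the next sentence: "The alternative hypothesis is that the frequency of seizures is $> 61\%$ or $< 19\%$ in our study", which the section explains as 21 points either side of 40%.

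Section 9.1 gives the hypothesis behind the test: "frequency of seizures in both treatment cohorts will be within 20% of published results" of the NICHD cooling trial. The synopsis (section 1.1) uses the same 20% for adverse events in general.

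For this test the plan gives no alpha, no sidedness, no lower rejection count, no true rate at which the 86% applies, and no confidence level or interval method for the 21%. Sections 9.4.1 and 9.4.4, which cover the safety analysis, do not supply them either.

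**The concern.** The power sentence ties 86% to a margin of 21 points, and the next sentence turns that margin into 61% and 19%. A reader will therefore take 86% as the power against a 21-point departure from 40%. The rule does not have that power upwards, and downwards it has practically none.

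This is the only stated test of the seizure hypothesis in section 9.1, and seizures are an adverse event of special interest. With 86% power at 61%, a result of 10 or fewer would occur only 14% of the time if the true rate were 61%, so it would be fairly strong reassurance. In fact it occurs 40% of the time. At the other end, 0 to 3 of 18 (at most 3/18 = 16.7%) falls in the stated alternative below 19% but does not reject.

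**Working it through.** **Inputs, all from section 9.2:** n = 18; null rate 0.40; reject if X ≥ 11; alternative above 0.61 or below 0.19; stated power 0.86; stated precision 21 points on each side of the point estimate. Assumption: the count is of infants with seizures, at most one per infant, and outcomes are independent, so X is binomial.

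**Step 1. Can the 86% be reproduced?** The power of a fixed count rule depends only on n, the cut-off and the true rate p. Alpha does not enter:

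P(X ≥ 11 | p) = Σ (k = 11 to 18) C(18, k) p^k (1 − p)^(18 − k)

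| True rate p | P(X ≥ 11) | Meaning |
|---|---|---|
| 0.40 | 0.0576 | one-sided type I error |
| 0.61 | 0.5979 | power at the stated upper boundary |
| 0.70 | 0.8593 | rounds to the stated 86% |
| 0.19 | 0.0001 | rejection at the stated lower boundary |

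The stated figure is reproduced at p = 0.70 and not at p = 0.61. The gap at 0.61 is 86 − 59.8 = 26.2 points, and the chance of not rejecting there is 1 − 0.598 = 0.402.

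**Step 2. Does another method give 86% at 61%?** A one-sample z-test of 0.40 against 0.61 with n = 18 gives 0.569 (one-sided 5%), 0.444 (two-sided 5%) and 0.705 (one-sided 10%). The normal approximation to the 11-of-18 rule gives 0.592 with continuity correction and 0.496 without. Neighbouring exact cut-offs at 0.61, with type I error at 0.40, are:

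- 10 or more: 0.765 (0.135)
- 9 or more: 0.884 (0.263)
- 12 or more: 0.408 (0.020)

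None gives 0.86.

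**Step 3. What would a lower cut-off cost?** Keep 11 or more and also reject at c or fewer. Total type I error = P(X ≤ c | 0.40) + 0.0576; power at 0.19 is essentially P(X ≤ c | 0.19).

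| c | P(X ≤ c at 0.40) | Total type I error | Power at 0.19 |
|---|---|---|---|
| 2 | 0.0082 | 0.066 | 0.307 |
| 3 | 0.0328 | 0.090 | 0.545 |

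**Step 4. The 21 points.** The wording is a distance on each side of the point estimate. The matching quantity is the largest distance from x/18 to either confidence limit, over x = 0 to 18. For Wald it is z√(0.25/18), reached at 9/18: 1.960 × 0.1179 = 0.231 at 95% and 1.645 × 0.1179 = 0.194 at 90%.

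| Method | 95% | 90% |
|---|---|---|
| Wald | 23.1 | 19.4 |
| Wilson | 23.1 | 19.4 |
| Exact (Clopper-Pearson) | 25.7 | 22.1 |

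All three 95% methods and the 90% exact interval exceed 21 points; 90% Wald and 90% Wilson stay within it.

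**The case against.** The strongest reply is that section 9.2 never says 86% is the power at exactly 61%. The alternative is a region, 70% lies inside it, and at 70% the rule gives 85.9%. A reader might infer a plain miscalculation; the documents do not support that, and an unstated design rate of 70% is the likelier source. This explains the number but does not repair the text: 70% is nowhere given, and the only margin named beside the power is 21 points. It also leaves the missing lower cut-off untouched.

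A rule that looks only for excess seizures is a reasonable safety design. That stands, and it is a reason to delete the lower alternative rather than build a test for it.

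On precision, a reader might infer that 21 is confirmed because half the total width is at most 21.0 points for a 95% Wilson interval and 20.9 for a 90% exact one. Neither interval is centred on the estimate, so half-width is not the quantity described; measured as worded, they reach 23.1 and 22.1. Nor can 21 be called false, since 90% Wald or Wilson stays inside it and the plan names no method.

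A reader might also infer that dose escalation or halting depends on the 86%. It does not. Those follow the independent monitor's review and the rule on drug-related serious adverse events (sections 9.4.4 and 10.1.6). The cohort size of 9 has its own pharmacokinetic justification.

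**Conclusion.** The power statement and the alternative are wrong as written. Power is 59.8% at the only upper alternative named, 26 points below the stated 86%, and reaches 86% only at an undocumented rate of about 70%. The rule rejects with probability 0.01% at 19%, so half of the stated alternative is untested. The 21% cannot be verified without a confidence level and method. The difference between 20% in sections 1.1 and 9.1 and 21 points in section 9.2 is minor wording, though sections 1.1 and 9.1 do not say whether 20% is relative or in points.

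The power figures are exact and rest on n = 18, the cut-off of 11 and independent infants; no choice of alpha changes them. The effect is confined to interpreting a secondary safety outcome. It should be fixed because the correction is cheap and the present text invites false reassurance from a non-significant result.

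**What to change.** 1. Restate section 9.2 as a one-sided rule: reject 40% if 11 or more of 18 infants have seizures; exact one-sided type I error 5.8%; power 60% at a true rate of 61% and 86% at 70%.
2. Delete the alternative below 19%. If it is kept, add a lower cut-off and disclose the cost: 3 or fewer gives 54% power at 19% with total type I error 9.0%; 2 or fewer gives 31% with 6.6%.
3. State the confidence level and method behind the 21%, and check it as the largest distance from the estimate to a limit.
4. In section 9.4.4, commit to reporting the seizure rate with its confidence interval, and say that non-rejection is not evidence that the rate is within 20% of the historical one.
5. Align the 20% in sections 1.1 and 9.1 with the 21 points in section 9.2, and say whether it is relative or in percentage points.

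The cost is wording in sections 1.1, 9.1, 9.2 and 9.4.4, and a less favourable stated power at 61%. A lower cut-off, if chosen, raises total type I error. No extra patients are needed and clinical management does not change.
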